9.1 Event counting for efficacy

All events occurring prior to or at the analysis cut-off date will be included in the efficacy analyses.

Only adjudicated and confirmed events will be counted in the primary and secondary analyses. Event information received after the analysis cut-off date will not be included in the primary and secondary efficacy analyses, but they will be included in the investigator reported event analysis.

For a patient who did not complete the study, i.e. who was lost to follow-up or withdrew consent, if the vital status for the patient can be retrieved from public information (or vital status can be confirmed by indirect contact), the last known alive date defined for the analysis will be the last alive date obtained from the retrieved information.

9.2 Variables

The variables defined in this section are only for the double blind period. The baseline referred to in the variable definitions below is always the double blind phase baseline, unless otherwise indicated. For variables related to changes at Month 8, Month 8 refers to Week 32.

Primary variable:

- Cumulative number of primary composite events, i.e., the composite events of (total) HF hospitalizations and CV death, for a given subject, over time.

Secondary variables:

- Change from baseline in KCCQ clinical summary score at Month 8;
- Change from baseline to Month 8 NYHA class;
- Time from randomization to first occurrence of composite renal endpoint event, defined as either:
 - Renal death, or
 - a 50% decline in estimated glomerular filtration rate (eGFR) relative to baseline, or
 - reaching end stage renal disease (ESRD);
- Time to all-cause mortality.

Exploratory variables:

- Cumulative number of events of the extended composite endpoint of CV death, total HF hospitalizations, total non-fatal strokes, and total non-fatal MIs, for a given subject, over time;
- Change in clinical composite assessment (NYHA, global patient assessment, and clinical events defined as CV death and HF hospitalization) at Month 8;
- Patient global assessment at Month 8;
- Changes from baseline in health-related QoL (assessed by the total score, clinical summary score, and individual scores of the sub-domains from the KCCQ and assessments of the EQ-5D for health status);
- Number of HF events per-subject;
- Number of total worsening HF events and CV death per-subject. A subject will be defined as having a CV death or worsening HF event when the subject has:
 1. CV death or
 2. A hospitalization for HF or
 3. Received intravenous (IV) decongestive therapy (IV diuretics, IV nesiritide or other natriuretic peptide, IV inotropes, and IV nitroglycerin [NTG]), and does not result in formal inpatient hospital admission, regardless of the setting (i.e. in an emergency room (ER) setting, in the physician's office, an outpatient treatment facility, etc.);
- Number of all-cause hospitalizations per-subject and number of cause specific hospitalizations per-subject;
- Number of days alive and out of hospital (DAOOH) at Month 12;

- Number of days alive and out of hospital (DAOOH) during the randomized, double-blind study period and percentage of DAOOH over potential follow-up time (defined as date of end of study minus date of randomization plus 1);
- Rate of change in eGFR (eGFR slope);
- Time from randomization to new onset diabetes mellitus (NODM);
- Time to new onset of atrial fibrillation (AF);
- Number of days staying in intensive care unit (ICU), number of stays in intensive care unit (ICU), number of re-hospitalizations for HF, and number of ER visits for HF;
- Indicator of 30 day HF rehospitalization (after a prior HF hospitalization during double blind phase);
- Number of rehospitalizations within 30 days after discharge;
- Time between HF hospital readmissions;
- Changes in pre-specified biomarkers (e.g., cardiac, vascular, renal, collagen, metabolism, and inflammatory biomarkers) from baseline to predefined time-points (in a subset of patients);
- Variables to characterize the PK of valsartan, AHU377, and LBQ657 at steady-state in patients receiving LCZ696 using population modeling and/or non-compartmental based methods;
- Change from baseline in Mini-Mental State Examination (MMSE) summary score at year 2 (week 96).

Among the variables above, some of them or their components need to be adjudicated to confirm the reported types and occurrences based on the unified criteria for analyses. The adjudication of these events is based on an adjudication process through an independent Endpoint Adjudication Committee. The following events will be assessed by the Endpoint Adjudication Committee during the study:

- All death events;
- Unplanned hospitalization for HF;
- MI;
- Stroke;
- Renal dysfunction (including occurrence of end stage renal disease);
- Others (new onset atrial fibrillation (NOAF), NODM)

In the analysis, as specified before, only adjudicated events will be utilized if the events included in the analysis are required to be adjudicated. However, in the sensitivity analysis, the investigator reported events may also be used.

As specified before, all events and endpoints occurred or measured prior to or at the specified analysis time-points (such as Month 8, Month 12, etc.), including the analysis cut-off date, will be counted, unless otherwise specified.

Censoring variables:

Number of events and time-to-event variable are usually subject to censoring. The censoring can be caused by withdrawal of consent, lost to follow-up, other competing events, or administrative reasons (interim or analysis cutoff date). Below are the rules for deriving censoring variables in the analyses (primary, secondary, exploratory):

- For all-cause death, the censoring will occur at minimum (date of withdrawal of consent, last known alive date, analysis cutoff date)
- For CV death, the censoring will occur at minimum (date of withdrawal of consent, last known alive date, analysis cutoff date, date when patient died for non-CV causes)
- For a non-mortality and non-composite endpoint, the censoring will occur at minimum (date of withdrawal of consent, date of lost to follow-up, analysis cutoff date, date when patient died)
- For a composite endpoint, the censoring will occur at the earliest censoring date among the components.

In some additional analyses, one may be interested in all events occurring before major protocol deviations. In such cases, the events occurred after having major protocol deviations need to be censored. The censoring variables are:

- Minimum (the censoring time defined for the primary, secondary, exploratory analyses, date of the first major protocol deviation).

9.3 Statistical hypothesis, model, and method of analysis

9.3.1 Primary analysis

All adjudication confirmed primary events occurred between randomization and the analysis cut-off date will be included in the primary analysis.

9.3.1.1 Analysis for primary endpoint

The primary efficacy endpoint of the study consists of the times to recurrent hospitalization due to heart failure and death time due to CV reasons during the patient's follow-up. The comparisons between two treatment groups will be made using statistical procedures which deal with such multiple event time observations. The semi-parametric proportional rates model (abbreviated as LWYY model) (Lin et al 2000) will be utilized for quantifying the treatment difference.

Specifically, let $\lambda_{ij}(t, x_{ij})$ be the individual rate of primary composite events for subject i in region j , given that the patient has not died from a CV reason at time t . It is dependent on the time from randomization (t) and treatment group (x_{ij}). Let $x_{ij} = 1$ if the subject is in the LCZ696 group and $x_{ij} = 0$ if the subject is in the valsartan group.

Under the proportional rates model, the individual rate function for the composite endpoint of CV death and total HF hospitalizations is assumed to be, $\lambda_{ij}(t, x_{ij}) = Y_{ij}(t)\lambda_{0j}(t)\exp(\beta_0 x_{ij})$, where $Y_{ij}(t) = 1$ if subject i in region j is at risk for HF hospitalization or CV death at time t and $Y_{ij}(t) = 0$ if subject i in region j is censored or died from a CV reason at time t – and $\lambda_{0j}(t)$ is the baseline rate function for the event in region j . ($Y_{ij}(t) = I(\min(T_{ij}, C_{ij}) \geq t)$, where T_{ij} and C_{ij} are CV death time and censoring time for subject i in region j . $I(\cdot)$ is an indication function.)

The primary hypothesis to be tested is, $H_{10}: \beta_0 \geq 0$ versus $H_{1a}: \beta_0 < 0$, where $\exp(\beta_0)$ is the relative risk or rate ratio (RR) of total hospitalizations for HF and CV death in the LCZ696 group relative to the valsartan group given the patient has not died from a CV reason at time t , which is assumed to be constant over time and across regions.

The primary hypothesis could be equivalently written as:

H_{10} : Rate ratio LCZ696/valsartan ≥ 1 versus H_{1a} : Rate ratio LCZ696/valsartan < 1 ,

A rate ratio < 1 indicates an effect in favor of LCZ696.

Note that $\exp(\beta_0)$ can also be considered as a ratio of two mean cumulative frequencies of a subject having hospitalizations for HF and CV death when the rate ratio is constant over time and CV mortality is balanced between treatment groups.

The primary hypothesis will be tested at a one-sided significance level of 0.024 adjusted for the interim analysis. The rate ratio and its 95% confidence interval will be estimated from the above proportional rates model through maximization of a partial likelihood score function. The resulting estimate of $\exp(\beta_0)$ is identical to the one described by Anderson and Gill ([Anderson and Gill 1982](#)), but unlike Anderson-Gill, a robust variance estimator (sandwich estimator) is used to account for the dependency of within subject events. Note that having CV death is not considered as a censoring variable, but as a primary endpoint event and a conditional factor in this analysis. The “conditional factor” means that the rate of the composite endpoint at time t is evaluated conditional on the patient being at risk of CV death at time t . Time to non-CV death will be considered as a censoring variable. Any censoring due to non-CV death is assumed to be non-dependent in the analysis.

The above presented analysis method based on LWYY provides a treatment comparison based on primary endpoint rate ratio conditional on not having died from a CV reason. A marginal interpretation of the estimates requires that any censoring of the primary composite events will be non-informative and may be challenging if there is an imbalance in CV mortality.

The LWYY analysis can be carried out using the following SAS code:

```
proc phreg data=primary_data covs(aggregate);  
    model (time_start, time_rec)*status_rec(0)=treat/ties=efron rl;  
    id sidla;  
  
run;
```

where `primary_data` is the input dataset, `time_start` is the previous event stop time and `time_rec` is the current event stop time, the censoring variable `status_rec` (0 for censored

and 1 for event) should take the value 1 if the last event is a CV death and 0 if it is censored for any non-CV death reasons for the given patient; `sid1a` is the subject ID.

As a supportive part of the primary analysis, the two components in the composite endpoint (total HF hospitalizations and CV mortality) will be analyzed separately to quantify the respective treatment effects and check the consistency between the composite and the components.

For the analysis of total HF hospitalizations component, occurrence of CV death can be regarded as semi-competing risk (informative censoring) and may introduce a bias in the treatment effect estimate for HF hospitalizations (dilution of effect size if the drug has a positive effect on both components). In order to address this concern and to account for the correlation between the two components, the joint modeling (frailty model) approach ([Cowling et al 2006](#)) will be used for the component analyses. The joint model is specified as follows.

$$\begin{aligned}\lambda_{ij}^H(t) &= Y_{ij}(t)\lambda_0^H \exp(\beta_0 x_{ij})\nu_{ij} \\ \lambda_{ij}^T(t) &= Y_{ij}(t)\lambda_0^T \exp(\gamma_0 x_{ij})\nu_{ij}^\alpha \\ \nu_{ij} &\sim f(\cdot)\end{aligned}$$

where $\lambda_{ij}^H(t)$ is the rate function of the total hospitalizations for HF for subject i in region j and λ_0^H is its constant baseline and $\lambda_{ij}^H(t)$ has a similar format as the model described above for the primary endpoint except for the multiplier ν_{ij} that is a subject-specific random effect factor (frailty); and $\lambda_{ij}^T(t)$ is the hazard function for the component of CV mortality for subject i in region j and λ_0^T is its constant baseline and $\lambda_{ij}^T(t)$ is a frailty proportional hazards model. The parameter α measures the association between $\lambda_{ij}^H(t)$ and $\lambda_{ij}^T(t)$. The frailty distribution $f(\cdot)$ is taken to be the Gamma distribution with shape = θ and scale = $1/\theta$. The parameters in the joint model, including the unknown power for the frailty, will be estimated through maximization of the corresponding likelihood. The model assumes that the correlation between total HF hospitalizations and CV death for each patient is completely explained by x_{ij} and the frailty and the two analysis variables corresponding to the two components are independent given the patient's frailty and x_{ij} .

For the analysis of CV death, it will be analyzed using Cox's proportional hazards model with a fixed treatment group factor and stratified by region. The analysis in the joint frailty model for this component, which is actually subject specific, will be considered as supportive for the analysis for CV death whenever an inference is needed for it.

In all the proposed analyses, it is acknowledged that the study will not be powered to achieve statistically significant results for the CV death.

The proposed joint frailty model assumes a constant baseline intensity and constant baseline hazard model for the recurrent HF hospitalization and CV death components, respectively. The marginal model for the recurrent hospitalizations for heart failure of this joint frailty model is a negative binomial model.

As a sensitivity analysis, the constant baseline intensity function λ_0^H and constant baseline hazard function λ_0^T will be replaced by piece-wise constant functions (i.e. multiple-step

functions). The number of steps in the step functions will be selected based on the Bayesian Information Criterion (BIC). The partitions of these constant step intervals can be obtained based on the equally-divided percentiles (Liu and Huang 2008).

The joint model will be estimated using SAS PROC NLMIXED. The below SAS code illustrates the program for a piece-wise constant intensity and hazard baseline function with 10 steps:

```
proc nlmixed data=data_joint qpoints=5 corr;
parms / data=inpar;
bounds r01 r02 r03 r04 r05 r06 r07 r08 r09 r10 h01 h02 h03 h04 h05 h06
h07 h08 h09 h10 alpha >=0;

/* g is Gamma distributed with mean 1 and variance 1/alpha*/
p=cdf('NORMAL', nu);
if p > .999999 then p=.999999;
g2=quantile('GAMMA', p, alpha);
g=g2 * 1/alpha;
/* baseline hazard and cum baseline hazard, recurrent events */
base_haz_r=r01*event_r1+r02*event_r2+r03*event_r3+r04* event_r4 +
r05*event_r5+r06*event_r6+r07*event_r7+r08*event_r8
+r09 * event_r9 + r10 * event_r10;
cum_base_haz_r=r01*dur_r1+r02*dur_r2+r03*dur_r3+r04*dur_r4 +
r05*dur_r5+r06*dur_r6+r07*dur_r7+r08*dur_r8+r09*dur_r9 +
r10 * dur_r10;
/* baseline hazard and cumulative baseline hazard for death */
base_haz_d=h01*event_d1+h02*event_d2+h03*event_d3+h04*event_d4 +
h05*event_d5+h06*event_d6+h07*event_d7+h08*event_d8+
h09 * event_d9 + h10 * event_d10;
cum_base_haz_d=h01 * dur_d1 + h02 * dur_d2 + h03 * dur_d3 +
h04 * dur_d4 + h05 * dur_d5 + h06 * dur_d6 + h07 * dur_d7 +
h08* dur_d8 +h09 * dur_d9 + h10 * dur_d10;
mu1= beta1 * trt + log(g);/* for recurrent event */
mu2= alpha1 * trt + gamma * log(g); /* for death event */
loglik1=-exp(mu1) * cum_base_haz_r;
loglik2=-exp(mu2) * cum_base_haz_d;
/*log likelihood for recurrent event */
if status_rec = 1 then loglik=log(base_haz_r) + mu1 ;
/*log likelihood for death */
if status_rec = 2 then loglik=loglik1 +log(base_haz_d)+mu2+loglik2;
/*log likelihood for censoring */
if status_rec = 0 then loglik=loglik1 + loglik2;
model time_stop ~ general(loglik);
random nu ~ normal(0, 1) subject = sid1a;
ods output ParameterEstimates=jm.est FitStatistics=jm.fit;
run;
```

where `data_joint` is the input dataset, `jm.est` and `jm.fit` for the parameter estimates and model fitted statistics. The dataset `inpar` contains the initial guesses for `r01-r10`, `h01-h10` and the other model parameters. The input dataset `data_joint` should include the values of event indicators `event_r1- event_r10` and `event_d1- event_d10` and durations `dur_r1- dur_r10` and `dur_d1- dur_d10`.

A non-parametric estimate of the primary endpoint event rates (Nelson-Aalen estimates) will be provided. Non-parametric estimates of conditional HF hospitalization rates (Nelson-Aalen estimates), given the patient has not died due to a CV reason, over time (Cook and Lawless 1997) and of unconditional HF hospitalization rates over time allowing for death as terminal event will be provided as well (Ghosh and Lin 2000).

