3.2 Rationale of study design

3.2.1 Target study population and rationale

The study population will consist of patients ≥ 50 years of age with a LVEF $\geq 45\%$ and evidence of structural heart disease (LAE or LVH), current symptoms of HF (NYHA class II-IV) and prior symptoms of HF requiring treatment with diuretic therapy. In addition, patients will have at least one of the following: (1) a hospitalization for HF within 9 months prior to enrollment and NT-proBNP >200 pg/ml for patients without AF or >600 pg/ml for patients with AF on Visit 1 ECG; **OR**, (2) NT-proBNP >300 pg/ml for patients not in AF or >900 pg/ml for patients in AF on Visit 1 ECG. These criteria should identify the target HFpEF population at risk for major CV events.

Structural heart disease (LAE and LVH) is a key diagnostic criterion for HFpEF in the most recent guidelines ([McMurray et al 2012](#)). Left atrial (LA) size (an integrative measure of left ventricular diastolic pressure) is independently associated with an increased risk of morbidity and mortality ([Zile et al 2011](#)). Including either LAE or LVH will help ensure a diagnosis of HFpEF. The EF lower boundary at 45% was selected to include a wide spectrum of patients for whom no proven therapy is currently available. Prior HF hospitalization and elevated NT-proBNP were the strongest independent predictors of mortality and subsequent HF hospitalization in the I-PRESERVE study ([Solomon et al 2007](#), [Komajada et al, 2011](#)). Patients with baseline AF are required to have higher NT-proBNP levels, as AF is strongly associated with higher levels of NT-proBNP ([McKelvie et al 2010](#)). The number of AF patients will be limited to approximately one third in the current study (based on the Visit 1 ECG) so that the proportion of patients with AF in the study will be representative of the HFpEF population ([Massie et al 2008](#), [Steinberg et al 2012](#), [West et al 2011](#)).

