6.6.3 NT-proBNP

NT-proBNP measurements will be performed by the central lab in all patients at Visits 1, 101/102 (whichever occurs first), 103, 199/201, 203 and 205. Only the Visit 1 NT-proBNP results will be reported to the investigator and the sponsor. All other measurements will be blinded to the site and the Novartis clinical study team.

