9.2 Patient demographics and other baseline characteristics

Baseline value is defined as the last non-missing assessment prior to the first dose of randomized study drug unless specified otherwise. This baseline is the randomized treatment epoch baseline.

Summary statistics will be provided by treatment group for demographics and baseline characteristics, including age, age group (<65 years vs. ≥65 years; <75 years vs. ≥75 years), sex, race, ethnicity, weight, height, body mass index (BMI), category of prior CV medication, prior HF hospitalization, NYHA class, NT-proBNP, and vital signs. BMI will be calculated as weight (kg) / height² (m²) from the collected height and weight at Visit 1 (Screening Visit). Continuous variables will be summarized using n, mean, standard deviation, median, minimum, and maximum. Categorical variables will be summarized using frequency and percentage.

The difference between treatment groups will be compared using the Chi-square test for categorical variables or using t-test for continuous variables. The p-values will be provided for descriptive purposes and will not be considered to define any formal basis for determining factors to be included in statistical models. If a substantial imbalance of treatment groups with respect to some variables does occur, supplemental analyses with addition of these variables in model may be performed to assess the potential impact on efficacy as appropriate.

The FAS will be the patient population for the above analyses.

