3.1 Subgroups

Subgroups will be formed for the analyses for the FAS or SAF depending on the parameters under consideration to explore the consistency of treatment effects and safety profiling between the subgroups and the overall population.

In general, subgroups will be defined based on baseline information. In this study, since we have a run-in phase to test patients' tolerability to the study drugs before they can enter the double-blind phase, we have defined two baselines ([Section 4](#)): the run-in baseline and the double-blind baseline. Subgroups may be formed using one of these baselines according to their analysis purposes.

In [Table 3-1](#), we have listed all subgroups defined for this study and the ways to derive them. In different analysis, such as efficacy analysis or safety analysis, a different subset of them will be selected. Also note that only important parameters or variables in these analyses may have subgroup analyses. The details about the parameters having subgroup analyses will be presented in the corresponding sections below. Also, additional subgroups may be formed later for regional or country-wise analyses per request for exploratory purposes.

Table 3-1 Specification of subgroups

Subgroup	Method of Derivation	Disposition /Background & demo. /Exposures	Efficacy (Primary and secondary)	Health economics (KCCQ and EQ-5D only)	Safety
Age groups: <65, ≥65; <75, ≥75 years	Screening	x	x	x	x
Gender	Screening	x	x		x
Race (Caucasian, Black, Asian, Other)	Screening	x	x		x
Region *	Derived (pooled countries or country), using	x	x	x	x

	Screening data				
Diabetic at baseline (yes/no)	Randomization (Derived)		x	x	
Baseline LVEF ≤ median, >median	Screening	x	x		
Atrial Fibrillation based on ECG at baseline: yes/no	Randomization		x	x	
Atrial Fibrillation based on prior history at baseline: yes/no	Randomization		x	x	
Baseline NT-proBNP: ≤ median and > median	Screening		x	x	
SBP ≤ median, >median	Screening		x		
Use of Aldosterone antagonist at baseline: yes/no	Randomization (Derived)		x	x	
ACEi intolerant: yes/no	Screening		x		
Baseline eGFR (<60 vs ≥60 mL/min/1.73 m ²)	Randomization (Derived)		x		
NYHA classification at baseline I/II vs III/IV	Randomization		x		
UK				x	

* **North America:** USA, Canada

Latin America (including Central America): Argentina, Brazil, Colombia, Guatemala, Mexico, Peru

Western Europe: Austria, Belgium, Denmark, Finland, France, Germany, Greece, Italy, Netherlands, Norway, Spain, Sweden, Switzerland, UK

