The post-randomized treatment phase (usually after unscheduled, permanent study drug discontinuation) begins after last study drug intake + 1 day and ends on the date last seen (or vital status confirmed by indirect contact).

Double-blind (DB) phase (Randomized treatment epoch)

The double-blind phase is the combination of the randomized treatment phase and the post-randomized treatment phase.

Baseline for run-in phase

The treatment run-in baseline is defined as the last available measurement prior to or at time of Visit 101 or Visit 102, whichever is earlier. For some parameters, values may be only collected at screening (Visit 1). For them the treatment run-in baseline will be at screening.

Baseline for double blind phase

The baseline for the double blind phase is defined depending on the parameter considered. In general, the baseline for the double blind phase is defined as the last available measurement during the LCZ696 *run-in* phase and randomization (generally Visit 199 or Visit 201). For the parameters that are not designated to have measurements collected during the LCZ696 run-in or randomization, the run-in baseline may be used as the baseline for the double blind phase. The following parameters will have the double blind phase baseline at randomization visit:

NYHA class, HF signs and symptoms, vital signs, waist/hip circumference, eGFR, safety laboratory values, endpoints, 1st morning urine (sub-study patients only), lab assessments, patient global assessment (it is assumed that patients will assess their health status comparing to that at randomization), KCCQ scores and EQ-5D assessments and MMSE.

The following parameters will have their double blind phase baseline measured only at screening visit (Visit 1), i.e., prior or at Visit 101 or 102:

Height, (HF, diabetes, liver, and other) medical histories, demography, echocardiogram, and inclusion/ exclusion criteria.

NT-proBNP will be collected in all patients at Visits 1, 101/102 (whichever occurs first), 103, 199/201, 203 and 205. Additional biological markers will be collected in a subset of patients. For these biomarkers, the baseline will be defined as values at Visit 101 or 102, whichever occurs first.

Unscheduled visit

Only for the analysis of safety laboratory evaluation will unscheduled measurements be taken into account. For efficacy evaluations, measurements from unscheduled visits will generally not be used, unless specifically specified.

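### The primary rates model adjusts for no baseline prognostic covariate, although the two predictors the protocol ranks strongest are collected before randomisation; pre-specified adjustment would give a small gain in precision at little cost

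*SAP*

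**What the plan says.** SAP 9.3.1.1 writes the event rate as a function of treatment, with a term that "is the baseline rate function for the event in region j". The sample code below it has treatment alone: "model (time_start, time_rec)*status_rec(0)=treat/ties=efron rl". Neither contains a patient-level prognostic covariate.

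Protocol 3.2.1 justifies the entry criteria on prognostic grounds: "Prior HF hospitalization and elevated NT-proBNP were the strongest independent predictors of mortality and subsequent HF hospitalization in the I-PRESERVE study". Protocol 6.6.3 has NT-proBNP measured centrally in every patient at Visit 1 and at later visits before randomisation. Protocol 9.2 lists "prior HF hospitalization, NYHA class, NT-proBNP, and vital signs" among the baseline characteristics to be summarised.

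Baseline adjustment of efficacy appears only in Protocol 9.2. If a substantial imbalance is seen, "supplemental analyses with addition of these variables in model may be performed to assess the potential impact on efficacy as appropriate". SAP 6.2 adds that comparability tests will not decide which variables enter the models. For the primary endpoint, the one covariate-adjusted analysis named in SAP 9.3.1.2 uses systolic blood pressure as a time-dependent covariate. By contrast, the KCCQ, NYHA and MMSE models in SAP 9.3.2 and 9.3.3 all adjust for the baseline value.

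**The concern.** In a recurrent-event analysis with strong between-patient variation, a baseline variable that explains part of that variation narrows the interval for the rate ratio. Here the plan names two such variables and collects them, then leaves them out of the primary model.

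Two things are at stake. One is a little precision on the primary rate ratio. SAP Table 13-1 gives power of 0.85 and 0.82 in the scenarios with an HF hospitalization rate ratio of 0.75, so a small gain is not worthless there. The other is the timing of choices. If adjustment is considered only after an imbalance has been seen, the covariates and their form are chosen with group data in view. In one simulation of this design (700 trials per setting), the adjusted and unadjusted models disagreed on significance at one-sided 0.024 in about 4% of trials, so a borderline result could be disputed.

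**Working it through.** **Inputs from SAP 13.1:** N = 4600, 1:1 allocation (Protocol 5.2); HF hospitalization intensity 0.00032/day and CV death hazard 0.000136/day before the uplift; gamma shape 0.193, so frailty variance 1/0.193 = 5.18; uniform enrolment over 2 years 5 months; minimum follow-up 2 years 2 months; one-sided alpha 0.025.

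**Step 1: reproduce the plan's power.** An independent-events formula does not apply. With 1847 events and a rate ratio of 0.778, the naive SE is 2/√1847 = 0.0465, which implies power of 0.9997. The simulated robust SE is 0.0701, so the variance is (0.0701/0.0465)² ≈ 2.3 times larger because events cluster within patients. Simulation is therefore needed.

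The uplifted intensities are not stated. Multiplying both by 1.08 gives 1636 events and power 0.940. Other readings give up to 1937 events and power 0.965. Raising them to land near the stated events gives, over 2000 runs:

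| HR death / RR HF hosp. | Plan: events, RR, power | Simulated: events, RR, power |
|---|---|---|
| 0.9 / 0.70 | 1847, 0.778, 0.95 | 1829, 0.777, 0.951 |
| 0.9 / 0.75 | 1882, 0.814, 0.85 | 1869, 0.815, 0.821 |
| 1.0 / 0.70 | 1846, 0.784, 0.94 | 1832, 0.784, 0.938 |
| 1.0 / 0.75 | 1885, 0.822, 0.82 | 1869, 0.819, 0.815 |

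The main scenario reproduces. The second row is about 3 points low here; the weakest covariate setting below, run with a different seed, returns 0.848. Monte Carlo error is about 0.5 to 0.9 points.

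**Step 2: add the covariates.** Effect sizes are assumptions, because the documents give none. Part of the frailty is assigned to standardised log NT-proBNP and to a prior-hospitalization indicator with 50% prevalence, with total frailty variance held at 5.18. Adjusted and unadjusted models are fitted to the same data, with HR 0.9 for CV death.

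| Assumed RR per SD log NT-proBNP / for prior HF hosp. | Residual frailty variance | Variance ratio, adjusted/unadjusted (RR 0.70) | Power at RR 0.70 | Power at RR 0.75 |
|---|---|---|---|---|
| 1.2 / 1.3 | 4.88 | 0.998 | 0.950 → 0.950 | 0.848 → 0.851 |
| 1.4 / 1.5 | 4.31 | 0.993 | 0.963 → 0.962 | 0.860 → 0.865 |
| 1.6 / 2.0 | 3.46 | 0.982 | 0.976 → 0.980 | 0.884 → 0.893 |
| 2.0 / 2.5 | 2.23 | 0.952 | 0.982 → 0.986 | 0.904 → 0.926 |

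At RR 0.75 the strongest setting has a variance ratio of 0.950. The variance reduction is thus 0.2% to 5%. The SE falls by 1 − √0.998 = 0.1% to 1 − √0.952 = 2.4%. The average rate ratio moves by at most 0.003 (0.810 to 0.807). Under the null, rejection at nominal 0.025 is 0.021 to 0.026 unadjusted and 0.019 to 0.028 adjusted.

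Two further simulations, parameterised by the SD of the covariates' combined log-rate effect (0.4, 0.6, 0.8, also assumed), give variance reductions of 0.6%, 1.8%, 4.2% and 0.7%, 1.8%, 4.2%.

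**Step 3: anchor the gain on the plan's own power.** Unadjusted power drifts upward across the settings in Step 2, so apply the variance ratio v directly: new power = Φ((1.96 + Φ⁻¹(P))/√v − 1.96).

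- P = 0.85, v = 0.998: (1.96 + 1.036)/0.999 − 1.96 = 1.039, power 0.851.
- P = 0.85, v = 0.95: 2.996/0.9747 − 1.96 = 1.114, power 0.867.
- P = 0.82, v = 0.95: 2.875/0.9747 − 1.96 = 0.990, power 0.839.

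The gain is about 0.1 to 1.9 points. In patients it is 4600 × 0.002 ≈ 9 to 4600 × 0.05 = 230.

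**The case against.** The strongest reply is that this is a preference. The unadjusted test holds its level, and the plan's power and type I error were simulated for that model. That stands, and it rules out one inference a reader might draw, that the omission biases or invalidates the primary result.

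Second, the size rests on assumptions. The prognostic claim comes from another trial, and inclusion criterion 7 truncates NT-proBNP with thresholds that depend on prior hospitalization and AF, so outside strength may not carry over. In the weaker settings the power change is within simulation error, and the larger simulated gains occur where unadjusted power already exceeds the plan's. This stands as a limit on size. Step 3 removes the last part of it and still leaves a gain of under 2 points at best.

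Third, adjustment is not free, and a reader might wrongly infer that it is. The rate ratio becomes conditional on the covariates and, with CV death terminating follow-up, need not equal the unadjusted one. A single NT-proBNP baseline is also needed. SAP Table 3-1 derives "Baseline NT-proBNP: ≤ median and > median" from Screening, while SAP Section 4 says "For these biomarkers, the baseline will be defined as values at Visit 101 or 102, whichever occurs first". Prior hospitalization needs one definition too: SAP Table 2-1 counts treatment of at least 12 hours with IV diuretics, which inclusion criterion 7a does not mention.

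Fourth, Protocol 9.2 already allows adjusted analyses after imbalance. It does, but optionally, without naming covariates or their form.

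Finally, the code line alone might suggest a model with treatment only. The equation does not support that, because region enters through its baseline rates. The missing region strata in the sample code is a separate matter.

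**Conclusion.** The point holds as a minor efficiency improvement. The primary model uses region and treatment but none of the baseline prognostic information that the protocol itself singles out. Pre-specified adjustment would cut the variance of the log rate ratio by about 0.2% to 5% and add 0 to about 2 power points, against a planned 82% to 85% at an HF hospitalization rate ratio of 0.75. The rate ratio would barely move. For scale, the SAP's document history records 300 extra patients (4300 to 4600) to raise power from 81% to close to 85%.

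This rests on assumed covariate effects, independent covariates, 50% prevalence of prior hospitalization, no modelling of region or non-CV death, and a total frailty matched in variance but not exactly gamma. AF was not simulated, so no gain is claimed for it. The documents support neither a claim of a substantial power loss nor one that the adjusted and unadjusted ratios are identical.

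**What to change.** Before unblinding, amend SAP 9.3.1.1 so that the primary LWYY model, stratified by region as in its equation, includes three covariates:

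- log NT-proBNP at Visit 1;
- HF hospitalization within 9 months before Visit 1 (yes/no), as defined in inclusion criterion 7a;
- AF on the Visit 1 ECG (yes/no), because Protocol 3.2.1 ties AF to higher NT-proBNP.

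State a simple missing-value rule, for example the pooled mean of log NT-proBNP computed blind to treatment. Report the unadjusted region-stratified model as a sensitivity analysis. If the sponsor prefers to keep the unadjusted model as primary, name the adjusted one in SAP 9.3.1.2 with the same details fixed.

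The cost is a short amendment and a few programming lines, with no new data. The text should say that the rate ratio is conditional on the covariates and that Visit 1 is the NT-proBNP baseline for this model. Timing needs care: SAP Amendment 3 is dated 28 May 2019, after the 30 April 2019 analysis cut-off, so the change should be documented as made blind.
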